3.3.1. Palliative and Supportive Care

Palliative and supportive care for disease-related symptoms will be offered as needed to all subjects in this study per the caring physician's judgment. These may be anti-emetics, anti-diarrhea agents, anti-abdominal cramping agents and blood products and blood transfusions as appropriate. Stomatitis may be treated at the PI's discretion

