- Subjects that have participated in any other investigative clinical trial in the past 4 weeks.

Dose and Dosing Regimen

The dose of METREXASSISTTM (TK-112690) will be 45 mg/kg administered parenterally over one hour in a clear, neutral, aqueous formulation (no organic chemical excipients). METREXASSISTTM will be given one hour before and 5 hours after the MTX treatment. The nutrient drink will be given one hour before METREXASSISTTM infusion. The MTX formulation will that traditionally used as standard-of-

care at a study site.

Test Product, Dose and Mode of Administration

- METREXASSISTTM (TK-112690 for Infusion) is a clear, sterile, neutral (pH=7.4), aqueous solution containing 5 mL of 100 mg/mL TK-112690.
- METREXASSISTTM is packaged as a 5 mL solution in a 10 mL flint glass vial with an elastomeric stopper held in place by an aluminum seal and flip-off cap. The concentration of TK-112690 in the solution is 100 mg/mL
- METREXASSISTTM will be administered as a continuous iv infusion over a duration of one hour in a volume of 250 mL normal saline.
- The nutrient drink, Fortasyn Connect[™] / Souvenaid[™], is commercially available as a 125 mL, 125 kcal solution. The drink is administered orally.
- The placebo is isotonic saline.

Reference Therapy or Comparator

Placebo-Isotonic saline

Follow-up

[figure not shown]
Subjects need to return at Day 1 of Week 6, which is two weeks from the last dose of the study drug.

Statistical Methods

- Safety: AEs, vital signs, physical examination data and clinical laboratory data will be analyzed using descriptive statistics with safety outcomes for patients in a dose group pooled & compared with patients in other groups.
- Mucositis: Scale data from individual doses groups will be analyzed using descriptive statistics.
- Surrogate Markers: Plasma concentration data evaluated for individual doses groups using descriptive statistics as well as compared with Surrogate marker data from the completed Phase 1bstudy.

INTRODUCTION

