3.1.2. DOSE MODIFICATIONS

[figure not shown]
Treatment will be withheld following grade 3 or 4 adverse events. Treatment may be restarted when the adverse events have recovered to \leq grade 2. Subjects in whom treatment is withheld for > 2 weeks will have treatment discontinued permanently.

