6.7. CLINICAL LABORATORY TESTS

6.7.1. Laboratory Parameters

Nitrite pH

Besides the Central Laboratory Tests, an in-house (at site) CBC, Kidney function test, Liver function test will be performed to qualify the subject for dosing with MTX, .Coagulation: (prothrombin time, PT, and activated partial thromboplastin time, PTT,tests will be performed at the Local laboratory associated with the clinical site as per schedule of events.

Subjects will be in a seated or supine position during blood collection. Clinical laboratory tests to be performed are included in **Table 10**. **Table 10**. **Central Laboratory Tests**

Hematology:SerumHematocrit (Hct)Hemoglobin (Hb)Mean corpuscular hemoglobin concentration (MCHC)Mean corpuscular volume (MCV)Platelet countRed blood cell (RBC) countWhite blood cell (WBC) count with differential	Blood urea nitrogen (BUN) C-reactive protein Calcium (Ca) Chloride (Cl) Creatinine Creatinine kinase Direct bilirubin Total bilirubin Total cholesterol (non-fasting) Total protein Triglycerides (non-fasting) Uric acid Gamma-glutamyltransferase (GGT) Globulin Glucose (Random)
Urinalysis :(will be performed by dipstick) Appearance Color Glucose Protein Occult blood	

Urine human chorionic gonadotropin: Females of childbearing potential only

Coagulation:

- Prothrombin time (PT)
- Activated partial thromboplastin time (PTT)

The laboratory measurements of clinical chemistry, hematology and urinalysis will be performed during screening (defined as baseline), on Day 0 and at 24 and 48 hours post each initial infusion of TK-112690 or Placeboas well as on Day 1 of Week6.

All laboratory measurements will be performed at a central laboratory. The laboratory will provide the PI and Tosk with test results including units, relevant reference ranges and updates as necessary. Laboratory measurements can also be performed at local sites for medical or informational reasons However; these measurements will not be considered part of the study record.

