6.7.4. Blood Samples

A blood sample for CBC, Kidney function test, Liver Function test determination will be obtained 24 hours or so before each MTX dose to assure the patient is suitable for treatment with this chemotherapeutic. The sample will be processed at the local laboratory associated with the clinical site, and the data provided to the PI, the CRO and Tosk.

6.7.5 Summary of Blood Samples to be obtained.

A summary of the blood samples to be obtained in the study is provided in **Table 11**.

Table 11. Nature and total volume of blood samples

Purpose	Size (mL)	Time	Total Volume (mL) / Patient
CBC, Kidney function test, Liver Function test	7	Pre-dose Weeks 1-4	28

Laboratory Test	14	Screening Day 0 Weeks 1-4 (24 and 48 hours) Week 6	154
Surrogate Markers	5	Weeks 1-4 (pre-dose, 5, 24 and 48 hours) Week 6	85
	•	Total	267

6.7.6 Processing Blood Samples.

Blood sample each will be collected per **Table 11** above and Schedule of Events (**Table 12**) for Laboratory, Surrogate Marker measurements in a heparinized tube and immediately placed on ice. Within 30 minutes of collection, plasma will be isolated by centrifugation at $4^{\circ}C/1000*g$ for 10 minutes.

- CBC, Kidney function test, Liver Function test (7 mL): This is a test prior to dosing to demonstrate that the patient can safely be treated with methotrexate. The test will be performed at the laboratory used by the clinical site.
- Laboratory Test samples (14 mL): The plasma for the laboratory tests will be split into two equal parts, transferred into polypropylene freezer vials and then frozen at -20°C to -70°C. One of the two vials will be used for the Laboratory Tests performed at the site and the other vial will be sent to the central laboratory.
- Surrogate Marker samples (5mL). The plasma for sample) will be transferred to a polypropylene freezer vial and then frozen at -20°C to -70°C.

Specific shipping instructions will be issued by the analytical laboratory performing the analyses. The heparinized tube and freezer vial will be labeled with study code, subject number, subject initials, date and sampling time points. The plasma samples will be stored at the center until the study coordinator arranges transport to the analytical sites.

Laboratory test will be performed both at the central laboratory except . Assays used to measure surrogate markers will be performed at Tosk, or a CRO engaged by Tosk.

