7.1. SCHEDULE OF EVENTS

Schedule of events are provided in **Table 12 below**. **Table 12.** Schedule of events (weekly cycle for 4 weeks and follow up at 6 week)

Englishting	Samooning	D. 0	Weeks 1, 2, 3, and 4					Week 6
Evaluation	Screening	Day 0	0h	5h	6h	24h	48h	Follow-up

Informed Consent ¹	Х							
I/E Criteria	Х							
Medical history ²	Х							
Test for drugs of abuse	Х	Х						
Physical examination ^{3,4}	Х	Х				X ⁵	X ⁵	Х
Vital signs and weight	Х	Х				X^6	X ⁶	X^6
ECOG	Х	Х						Х
Pregnancy test (females)	Х	Х						Х
12-Lead ECG	Х					Х		
Laboratory tests ⁷	Х	Х				Х	Х	Х
Randomization		Х						
CBC, Kidney function test, Liver Function test		X^8						
Nutritional supplement			X ⁹					
TK-112690/placebo treatments ¹⁰			X^{10}		X ¹³			
MTX treatment			X ¹¹					
Surrogate marker sample			X ¹²	Х		Х	Х	Х
Mucositis evaluation ¹⁴		Х				Х	Х	Х
Disease Status	Х							Х
AEs assessment				Х		Х	Х	Х
1 To be obtained before any	study-related	activities at	e perform	-d				

¹ To be obtained before any study-related activities are performed.

² Include a review of previous/ongoing medications for 180 days prior to enrollment.

³ Complete examination, including assessments of the skin, head, eyes, ears, nose, throat, neck, thyroid, lungs,

heart, abdomen, lymph nodes, extremities, and body weight.

⁴ Height will be measured at screening only.

⁵ Partial examinations to update findings from the examination performed at screening.

⁶ Include blood pressure, pulse, respiratory rate and temperature.

⁷ Includes serum chemistry, hematology (including coagulation), urinalysis; Hepatitis B/C & HIV only at screening

⁸ CBC, Kidney function test, Liver Function test at clinical site can be performed anytime within 24 hours of a methotrexate treatment (NEEDED FOR ALL MTX TREATMENTS, EG, TREATMENTS ON WEEKS 1, 2, 3, AND 4, TO VERIFY OK TO DOSE MTX)

⁹One hour before TK infusion/placebo

¹⁰ Beginning of TK-112690/placebo infusions is 0 hours. Dose is 45 mg/kg.

^{11 45} mg/m² one hour after TK-112690/placebo infusion.

¹² Pre-dose control samples for surrogate marker measurements.

¹³6 hours after TK-112690/placebo treatment, ie, 5 hours post MTX treatment

¹⁴See Section 20.6 for mucositis assessment scales.

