10.3.1. Incidence of Adverse Events

Adverse events will be classified and graded according to the NCI Common Terminology Criteria for Adverse Events (CTCAE), version 3.0.

The primary safety analysis using descriptive statistics will include summaries of incidence rates, severity, and type of adverse events; summary of changes in subjects' clinical laboratory results; and summaries of the number of toxicity grades for laboratory and non-laboratory data.

Adverse events will be coded using the MedDRA adverse event dictionary. Frequency of treatment emergent adverse events will be calculated for each body system, by preferred term, by treatment group, for number of subjects and proportion reporting the event. The severity of the adverse events and the relationship to study medication will be summarized for each body system and preferred term by treatment group. Withdrawals due to adverse events will be summarized for each body system and preferred term by treatment group.

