10.3.2. Laboratory Data

The number and percentage of subjects with laboratory abnormalities at the screening visit and the final visit (or early withdrawal) will be tabulated.

Descriptive statistics (number of observations, mean, standard deviation, minimum, median and maximum values) will be calculated for clinical laboratory tests (hematology, serum chemistry, and urinalysis) at applicable visits.

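### The laboratory abnormality table counts patients only at screening and the final visit, so a low blood count in Weeks 1–4 that is corrected by Week 6 is not counted in that table

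*Combined protocol and SAP*

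**What the plan says.** The rule is the first sentence of Section 10.3.2: "The number and percentage of subjects with laboratory abnormalities at the screening visit and the final visit (or early withdrawal) will be tabulated". The same section adds the number of observations, mean, SD, minimum, median and maximum for each test at the applicable visits.

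Section 10.3.1 places laboratory results in the primary safety analysis. It plans a summary of changes in laboratory results and "summaries of the number of toxicity grades for laboratory and non-laboratory data". It does not say whether the grade is the worst per patient, or which visits and samples contribute.

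The Study Synopsis (Follow-up) fixes the final visit: "Subjects need to return at Day 1 of Week 6, which is two weeks from the last dose of the study drug".

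Two provisions let a patient with a low count be corrected and carry on. Section 3.3.1 allows "blood products and blood transfusions as appropriate". Section 3.1.2 withholds treatment after a grade 3 or 4 adverse event and then says "Treatment may be restarted when the adverse events have recovered to" grade 2 or lower.

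A local blood count before each methotrexate dose is also mandatory. Table 12, note 8 marks it "NEEDED FOR ALL MTX TREATMENTS", and Section 6.7.4 has "the data provided to the PI, the CRO and Tosk".

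**The concern.** Central haematology is drawn at 24 and 48 hours in every treatment week, but the only summary that is clearly a count of patients with abnormal values ignores those draws for anyone who completes. A patient who is low in Week 2 and normal at Week 6 is recorded as not abnormal. The by-visit minimum can show that somebody was low, but not how many patients were low in each arm. By-visit means can include values taken after a transfusion.

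Safety and tolerability are the secondary objective, and this is the drug's first placebo comparison in patients. Blood counts are also where the harm in Phase 1b was concentrated. Sections 1.5.2.3 and 1.5.2.7 report six Grade 3/4 events, five of them haematological. Four of 25 patients discontinued for anaemia, and the two deaths were from febrile neutropenia and pancytopenia. All were assessed as unrelated to study drug, but Phase 1b had no control arm. If low counts differ between the arms here, the laboratory abnormality table may not show it.

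**Working it through.** **Reproducing the sampling schedule (Table 11, Section 6.7.5)**

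- Central laboratory: screening 1 + Day 0 1 + 4 weeks × 2 (24 h and 48 h) + Week 6 1 = 11 samples. 11 × 14 mL = 154 mL, as stated.
- Local pre-dose tests: 4 × 7 mL = 28 mL, as stated.
- Surrogate markers: 17 × 5 mL = 85 mL, as stated.
- Total: 28 + 154 + 85 = 267 mL, as stated.

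**What the abnormality table uses for a completer**

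- All central samples: screening and Week 6, so 2 of 11 (18%).
- Post-dose central samples: 8 + 1 = 9, of which the table uses 1 (1/9 = 11%).
- Weeks 1–4 central samples: 0 of 8.
- If the three local counts before doses 2, 3 and 4 are added: 9 + 3 = 12 post-dose results, of which the table uses 1 (8%). The central figure of 1 of 9 is the safer one, because the plan does not say that the local results are analysed.

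**Where a low count in Weeks 1–4 would appear**

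| Course of the patient | Abnormality table (10.3.2) | Adverse event tables (10.3.1) |
|---|---|---|
| Withdraws while low | Counted, from the withdrawal sample (8.2) | Should appear if the value led to stopping (9.1.2) |
| Dose held, restarted, normal at Week 6 | Not counted | Should appear (3.1.2, 9.1.2) |
| Transfused for a clinical condition, continues, normal at Week 6 | Not counted | Should appear (9.1.2) |
| Judged clinically significant by the investigator, normal at Week 6 | Not counted | Should appear (9.3.3) |
| Untreated, no delay, not judged significant, normal at Week 6 | Not counted | Does not appear (9.1.2) |
| Still low at Week 6 | Counted | As above |

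The fifth row is the gap that no other table clearly covers. Such a patient contributes to the by-visit statistics and may contribute to the grade summary in Section 10.3.1, but neither is defined as a count of patients by worst value.

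**What cannot be computed.** The documents give no frequency for low counts that are corrected without treatment, delay or a judgment of significance. The four Phase 1b discontinuations for anaemia (4/25 = 16%) do not supply it: in this trial such patients would have a withdrawal sample, which enters the table.

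**The case against.** The strongest reply is that the plan already has a laboratory count without the two-visit limit. The toxicity-grade summary in Section 10.3.1 names no visits, and Section 10.1 presents categorical variables as counts and percentages. On that view only a table specification is missing. This is largely right, and it is why the point is small. But without a per-patient worst-grade rule, the summary could count grades per sample, per visit or per patient, and could or could not include on-treatment values.

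A second reply is that the provisions for holding and treating patients themselves generate adverse event records. This stands. A reader might infer that transfused or held patients disappear from the safety analysis. The documents do not support that: Sections 3.1.2, 9.1.2 and 9.3.3 should bring them into the adverse event tables by arm.

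Third, Section 3.3.1 only permits transfusion, which is not a defect. Transfusions are captured as concomitant therapy with dose, dates and indication (Section 3.3). This stands too; the evidence for the point is the first sentence of Section 10.3.2.

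Fourth, it is tempting to read Phase 1b as an example, because Section 1.5.2.7 found no overall haematology concern despite the Grade 3/4 events. It is not one. Figures 7–11 in that section use pre-dose and Weeks 1–4 values, not a screening and final table, and nothing shows that transfusion explains the contrast.

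Finally, a reader might conclude that the pre-dose local counts fall outside the study record. Section 6.7.1 excludes local results from it, but in the context of optional testing: "Laboratory measurements can also be performed at local sites for medical or informational reasons". The mandated pre-dose count is a different item, and its results go to the CRO and the sponsor (Section 6.7.4). Its status is unsettled rather than excluded.

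**Conclusion.** The point holds for one table. For completers, the abnormality count in Section 10.3.2 uses 1 of 9 post-dose central samples and none of the 8 from Weeks 1–4, so a low count corrected by Week 6 is not counted there. These fractions follow directly from Table 11 and assume only that all scheduled samples are taken.

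Not counted in the table does not mean lost to the analysis. Patients who withdraw while low are counted, and held, treated or clinically significant cytopenias should reach the adverse event tables. What remains is mainly untreated lows that cause no delay and are not judged significant. Their number, and any resulting distortion of the difference between arms, cannot be derived from the documents. The study is exploratory and descriptive with 22 patients, and no efficacy result depends on this. It is a minor point, worth acting on because the better table uses data already collected, in the organ system where Phase 1b harm was concentrated.

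**What to change.** Keep the screening and final table and the by-visit statistics, and add to Section 10.3.2:

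1. By arm, the worst post-baseline CTCAE grade per patient for haemoglobin, platelets and neutrophils, from Week 1 to Week 6 or withdrawal. Show it as a shift from baseline and use all scheduled central samples. Section 6.7.1 defines screening as baseline. Name one CTCAE version, since Section 9.1.1 gives 4.0 and Section 10.3.1 gives 3.0.
2. As a supplement, the same table with the mandated pre-dose local counts included, and a statement that these are entered in the database for this purpose. They are the only scheduled counts between 48 hours after one dose and the next dose.
3. A list by arm of patients given blood products, with product, dates and indication, from the concomitant-therapy CRF (Section 3.3).

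The worst value should not be restricted to samples taken before a transfusion: the CRF specifies dates of use, not times, so the order of a sample and a transfusion on the same day could not always be established. Transfusion practice stays as it is.

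The cost is a few lines of text, one small table with its supplement, a listing, and entry of local results that already reach the CRO and the sponsor. The laboratory summary may look less favourable. No visit, sample or treatment rule changes.

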3.4. RESTRICTIONS

3.4.1. Prior Therapy

Participation in another clinical trial within 4 weeks of dosing is not allowed.

3.4.2. Fluid and Food Intake

There are no protocol-mandated restrictions with respect to ingested fluids and food.

3.4.3. Subject Activities and Restrictions

There are no specific restrictions in physical activities.

3.5. RANDOMIZATION AND BLINDING

The Phase 2a study will be partially blinded. The patient and investigator will be blinded as to whether TK-112690 or placebo is administered. The CRO, sponsor, and site pharmacist will know whether the patient was administered active drug or placebo.

A list providing randomization, active drug and placebo, for each of the 22 subjects will be prepared (List A). Another list will provide randomization for 8 additional subjects if additional subjects are enrolled (List B). Both lists will be kept by the CRO.

A designated person or Pharmacist will prepare the TK-112690 treatments by adding either active drug or placebo into 250 ml 0.9% sodium chloride iv bottle (**Appendix 3**). Whether active drug or placebo is added will reflect the subject number and the randomization suggestion made in the Randomization List for that subject number. The CRO will provide the designated person or pharmacist with vials re-labelled to maintain the partial blind. The randomization will be done by the CRO or a third-party vendor.

3.6. NUMBER OF SUBJECTS IN THE STUDY

A total of 22 subjects will be recruited over a period of 10 months.

3.7. CENTERS

This is a multi-center study conducted within India across various geographical regions in India. At least 3 centers are planned.

4.0. STUDY POPULATION

4.1. TARGET POPULATION

Subjects considered for enrollment will be selected from subjects presenting with a confirmed diagnosis of local, advanced, recurrent, metastatic SCCHN for which MTX at a dose of 45 mg/m^2 is the scheduled therapy.

4.2. INCLUSION CRITERIA

- Male and female subjects over 18 years old with a histologically or cytologically confirmed diagnosis of locally residual, recurrent or metastatic SCCHN.
- Subjects must have a histologically confirmed diagnosis SCCHN (any stage).
- Subject must have failed at least onecourses of non-MTX chemotherapy or one coursenon-MTX chemotherapy and chemo radiation for treating their SCCHN.
- No prior systemic treatments for cancer (chemotherapy and/or radiotherapy) within 4 weeks of dosing.
- Eastern Cooperative Oncology Group (ECOG) performance status 0 to 2.
- Must have a life expectancy of at least 6 months.
- History of brain metastases allowed if disease has stabilized or improved after radiation and/or craniotomy.
- No active angina or uncontrolled arrhythmia.
- No other concurrent, active, invasive malignancies.
- No detectable infection including hepatitis B/C and HIV.
- No pregnant or nursing females. Women of childbearing potential must have a negative serum β-hCG pregnancy test at screening and must use medically acceptable methods of birth control. Acceptable methods of birth control include oral or transdermal contraceptives, condoms, spermicidal foam, IUD, progestin implant or injection, abstinence, vaginal ring, or sterilization of partner. The reason for non-childbearing potential, such as bilateral tubal ligation, bilateral oophorectomy, hysterectomy, or post-menopausal for ≥ 1 year, must be specified on patient's source documents (medical history file) and CRF.
- Must have adequate organ and immune function as indicated by the following laboratory values:

Parameter Serum creatinine *Laboratory Values* ≤1.5 x ULN

CONFIDENTIAL Tosk, Inc

Estimated creatinine clearance	≥45 mL/min
Total bilirubin	≤2.0 mg/dL (≤34.2 μmol/L)
AST (SGOT) & ALT (SGPT)	≤3 x ULN
Absolute granulocyte count	$\geq 1.5 \text{ x } 10^9 \text{ cells/L}$
Platelets	$\geq 100,000/\mu L$

• Be able to read or understand, and provide a signature/thumb impression on the Informed Consent Form (ICF) before entering into the study.

